5. DESCRIPTION OF PARTICIPANT CHARACTERISTICS

5.1. Disposition

A flow of patients through the trial will be summarised in a CONSORT diagram (Figure 1 and Figure 2) that will include the eligibility, exclusion, number of patients randomised to the two treatment groups, loss to follow up and the number of patients analysed.

5.2 Baseline characteristics

Baseline questionnaires will be completed by patients. These data will be summarised in

Table 1 - Table 3.

As well as the baseline outcomes, demographic variables will be summarised at baseline. These demographic variables include age, sex, marital status, living arrangement, ethnic group, a measure of deprivation and level of education. The demographic variables will be summarised by treatment group, trial centre and overall to inform us of the demographic of the trial population and to check balance between treatment groups and trial centres.

Age and sex will be summarised between patients who we screened vs randomised patients to see if the population of randomised patients reflects a similar population to those who we screened.

6. ASSESSMENT OF TRIAL QUALITY

6.1. Eligibility checks

The number of patients who were assessed and were not eligible for participation in the trial will be described in **Table 4**. The STAR trial eligibility criteria have been designed to minimise patient risk. The reason for exclusion will also be recorded in **Table 4**.

6.2. Data validation

The system will incorporate data entry and validation rules to reduce data entry errors, and management functions to facilitate auditing and data quality assurance. We will use a secure, web-based data collection platform (REDCap) which will be developed, validated, hosted and supported by the University of Bristol. Named blinded assessors perform data completeness checks of data and contact patients if there is missing data in their

questionnaires. This will reduce the amount of missing data as patients will have the opportunity to complete missing items over the phone. This may also be an opportunity to clarify any misunderstandings in the questionnaire. It is important for these telephone calls to be done by a member of a different trial centre team so that the researcher who phones the patient is unaware of the treatment group allocation. This is intended to minimise bias.

6.3. Trial completion

Completion rates of questionnaires will be recorded in **Table 5** and **Table 8**. Withdrawals are summarised in **Table 9** and **Table 10** at different time points (6 months and 12 months) and the reasons for withdrawal will also be recorded in **Table 9** and **Table 10**. Patients who withdraw throughout the trial will contribute data up to the point of withdrawal providing permission is given to use previously collected data. Data missing from those patients who withdraw will be imputed in the mice analysis.

6.4. Compliance

A complier to treatment is defined as a patient in the intervention arm who attends the assessment clinic or a patient in the control arm who complies with usual care (all patients in the control arm). Since non-compliance numbers are likely to be low, we set a rule to decide if we will use CACE analysis. If compliance is close to 100% then ITT analysis will be very similar to CACE analysis and so the latter will not be (additionally) informative.

If compliance is greater or equal to 95%, we will rule out the need for using CACE analysis. For compliance between 85% and 95% we will consider carrying out CACE analysis depending on the extent and pattern of adherence. For compliance below 85% we will use CACE analysis. Compliance rate will be recorded in **Figure 2**.

Compliance is recorded in **Table 46** by site and in total.

Descriptions of the number of follow up calls that the intervention group patients receive will be presented by site and in total. The time to first follow-up call will also be summarised by site and in total. These summaries can be found in **Table 47.**

6.5. Protocol deviations

When identified, protocol deviations will be detailed on the appropriate standardised form and stored in the CRF [protocol deviation form]. The form will also be scanned and sent to the co-ordinating centre for review by the Chief Investigator. All protocol deviations will be reported to the Trial Steering Committee at meetings.

Number of protocol deviations and their nature will be recorded overall, over trial centre and over treatment group. This will be presented in **Table 11 - Table 12.**

6.6. Specify & justify changes made to the planned statistical analyses

Any adjustment to the statistical analysis plan will be logged in Table 51.

7. ANALYSIS OF EFFECTIVENESS

7.1 Statistical analysis

STATA version 15.1 will be used for all statistical analysis.

Continuous variables will be summarised using the mean and standard deviation (SD) (or median and inter quartile range (IQR) if the distribution is highly skewed), and categorical data will be summarised as numbers and percentages.

7.2. Summary statistics

The primary and main secondary outcomes will be summarised by mean (SD) or median (IQR) at each time point of baseline, 6 months and 12 months by intervention allocation group. The percentage of missing outcomes at each time point will be reported.

The mean BPI subscales at baseline, 6 months and 12 months will be plotted in a line graph along with confidence intervals marked at each time point. This will be split by each intervention allocation group.

A summary of the primary and secondary outcomes can be seen in Table 13.

7.3. Primary analysis

The primary and main secondary analyses will be conducted using the ITT principle (that is, comparisons of groups as allocated) using the appropriate regression model. Assumptions for each regression will be checked to make sure the correct method of analysis is being used.

Each of the co-primary outcome measures, BPI Severity and BPI Interference scales, will be analysed to compare treatment groups using linear regression. The models will be adjusted for trial centre as a fixed effect and baseline BPI pain scores. Estimates will be calculated of the effect that intervention has on each of the BPI scores compared with usual care. Primary analysis will be adjusted for variables which are imbalanced at baseline to see if this makes a marked difference to the unadjusted primary analysis.

Results from the primary analysis will be presented in **Table 14**.

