1. INTRODUCTION & PURPOSE

This document details the rules proposed and the presentation that will be followed, as closely as possible, when analysing and reporting the main results from the STAR Trial.

The purpose of the plan is to:

- Ensure that the analysis is appropriate for the aims of the trial, reflects good statistical practice, and that interpretation of a priori and post hoc analyses respectively is appropriate.
- 2. Explain in detail how the data will be handled and analysed to enable others to perform the actual analysis in the event of sickness or other absence.
- 3. Protect the project by helping it keep to timelines and within scope.

Additional exploratory or auxiliary analyses of data not specified in the protocol are permitted but fall outside the scope of this analysis plan (although such analyses would be expected to follow Good Statistical Practice).

The analysis strategy will be made available if required by journal editors or referees when the main papers are submitted for publication. Additional analyses suggested by reviewers or editors will, if considered appropriate, be performed in accordance with the Analysis Plan, but if reported the source of such a post-hoc analysis will be declared.

Editorial changes

Amendments to the statistical analysis plan will be described and justified in the final report of the trial in **Table 51** of this document.

Tables and figures

Throughout this document references are made to any skeleton tables and figures to be used in the reporting of the trial (e.g. **Figure F1** or **Table T1**). Such tables and figures can be found in **Appendix A** of this document and are intended as a guide for trial reporting. Final versions of the tables/figures may differ, tables may be combined, and/or their layout or numbering may evolve. However, the content will be consistent with **Appendix A**.

In this document, references to the protocol refer to "version 9, 04-02-2019".

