3.6. Randomisation procedures

After patients have provided written, informed consent to participate and have completed and returned a baseline questionnaire, they will be randomly allocated to the STAR pathway or usual care. Randomisation will occur as soon as possible after the baseline questionnaire is received by the research team. Randomisation with allocation concealment will be conducted remotely via the Bristol Randomised Trials Collaboration using a web-based randomisation system. Randomisation will take place on a 2:1 basis to ensure that the intervention service is running at sufficient capacity to enable a pragmatic assessment of its effectiveness and, particularly, cost-effectiveness. If the intervention is operating to a sufficient degree of capacity per-protocol and CACE analyses will be more reliable and have higher power. To ensure reasonable balance between the two treatment groups, allocation will be minimised by pain in the replaced knee (assessed with both the Brief Pain Inventory Severity and the Brief Pain Inventory Interference Scales – these scores are both categorised using tertiles of STAR PACE data for these scores) and stratified by orthopaedic centre. Randomisation will be performed by a member of the research team at the co-ordinating centre and the local researcher at each site will then inform participants of the result.

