7.4.2 Secondary outcomes

The secondary outcomes will be analysed using appropriate regression models in a similar manner to the primary analysis. The models will adjust for trial centre, baseline BPI pain score and also the baseline scores of the outcome for which it is modelling. A summary of the primary and secondary outcomes can be seen in **Table 13.** Further adjustment for any observed baseline imbalance will only be made for secondary outcomes in the unlikely event that such adjustment had a material effect on the results for the primary outcomes, or if there is a particular cause for concern as a consequence of a known strong relationship between a specific outcome and an individual variable demonstrating (chance) imbalance at baseline.

Results from the secondary analysis will be presented in Table 16.

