9.4. Primary outcome results

Table 14: Primary outcome table

	Usual	care		Intervention					
	N	Mean	SD	N Mean SD			Difference	95% CI	P-value
							in means ¹		
BPI Severity									
BPI									
Interference									

¹ Adjusted for trial centre and baseline OKS

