9.5. Secondary outcomes results

Table 15: Secondary analysis – adjusting for 'time to assessment clinic'

	Usual	care		Intervention					
	N	Mean	SD	Ν	Mean	SD	Difference	95% CI	P-value
							in means ¹		
BPI Severity									
BPI									
Interference									

¹ Adjusted for trial centre and baseline OKS and 'time to assessment clinic'

Table 16: Secondary outcomes tables

	Usual care		Interve	Intervention		Difference in	95% CI	P-value	
		1				means		-	
	Ν	Mean	SD	Ν	Mean	SD			
BPI Severity									
BPI Interference									
OKS									
DN-4									
PainDETECT									
Pain Catastrophizing scale									
PaSol: Solving Pain									
PaSol: Meaningful life									
PaSol: Acceptance of pain									
PaSol: Belief in solution									
Patient Satisfaction									
ICECAP-A									
Short form-12									
HADS: Anxiety									
HADS: Depression									
Section A: Question 5									
Section D: Question 8									
Section L: Question 5									
				N	Odds ratio ¹	95% Cl	P-value		
Body Map (CWP(M))]	

¹ Adjusted for trial centre and baseline OKS

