9.6. Sensitivity analysis for primary endpoint

Comparison of results of ITT analysis of complete cases with ITT analysis where missing data were imputed using "best" and "worst" case scenarios and the method of mice for primary outcome of **BPI Severity Score**. *Table 17:Sensitivity analysis for missing data*

	Ν	Difference in means ^a	95% CI	p-value
Complete case				
"Best" case scenario				
"Worst" case scenario				
mice				

^{*a}* Adjusted for trial centre and for baseline OKS

Comparison of results of ITT analysis of complete cases with ITT analysis where missing data were imputed using "best" and "worst" case scenarios and the method of mice for primary outcome of **BPI Interference Score**.

Table 18: Sensitivity analysis for missing data

	Ν	Difference in means ^a	95% CI	p-value
Complete case				
"Best" case scenario				
"Worst" case scenario				
mice				

^a Adjusted for trial centre and for baseline OKS

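### The primary-analysis text adjusts for baseline BPI, but the footnote of the table that reports that analysis says baseline OKS

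*SAP*

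**What the plan says.** SAP section 7.3 analyses BPI Severity and BPI Interference by linear regression and fixes the covariates: "The models will be adjusted for trial centre as a fixed effect and baseline BPI pain scores". It then names the place of reporting, "Results from the primary analysis will be presented in" Table 14. In section 9.4 the footnote on the difference in means in Table 14 reads "Adjusted for trial centre and baseline OKS".

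The same wording follows the co-primary outcomes elsewhere:

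- Table 15 (section 9.5), the primary analysis repeated with clinic timing: "Adjusted for trial centre and baseline OKS and 'time to assessment clinic".
- Tables 17-18 (section 9.6), missing-data sensitivity: "Adjusted for trial centre and for baseline OKS".
- Tables 30-31 (overlap with other trials) and Tables 32-33 (per protocol and CACE): the same footnote.

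For secondary outcomes, section 7.4.2 says: "The models will adjust for trial centre, baseline BPI pain score and also the baseline scores of the outcome for which it is modelling". The footnotes of the secondary-outcome tables again give centre and baseline OKS.

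Section 1 describes the shell tables as a guide whose layout and numbering may change, but adds: "However, the content will be consistent with" Appendix A.

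**The concern.** The covariate set is part of the definition of each co-primary estimate. The text and the footnote of the table it points to give two different sets for one analysis, so the estimate, confidence interval and p-value depend on which is followed. Section 1 also wants the plan to be usable by a stand-in analyst, and that person would find two models and no rule of precedence. An analyst who followed the footnotes would leave out the outcome's own baseline and both pain scores used in the minimisation. A choice left open until the data are in can be made with the results in view.

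**Working it through.** **1. The statements side by side**

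| Analysis | Text | Table footnote |
|---|---|---|
| Co-primary | 7.3: centre, baseline BPI | Table 14: centre, baseline OKS |
| Co-primary with clinic timing | 7.4.1: primary model plus time to clinic | Table 15: centre, baseline OKS, time to clinic |
| Co-primary sensitivity | 7.6.1 repeats the primary analysis; 7.6 and 7.6.2 name no other covariates | Tables 17-18, 30-33: centre, baseline OKS |
| Secondary | 7.4.2: centre, baseline BPI, own baseline | Tables 19-29, 34-44: centre, baseline OKS |

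Two qualifications apply to the secondary tables. In Table 16, as the text was extracted, the footnote marker sits only on the odds ratio. In Tables 19 and 34 OKS is the outcome, so the footnote there omits BPI but does not name a wrong covariate.

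**2. Which version the rest of the SAP supports**

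- Section 3.6: "allocation will be minimised by pain in the replaced knee", measured by BPI Severity and BPI Interference, with stratification by centre. OKS plays no part.
- Section 7.6.4: the repeated-measures model uses the baseline of the outcome.
- Section 4.3: so does the imputation model.
- OKS appears in the text as a secondary outcome (section 4.2) and as a subgroup interaction variable (section 7.7.2). No main-model text makes it an adjustment covariate.
- The amendment log (Table 51) records no change of covariate.

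**3. The stated power (section 3.7)**

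Inputs: 380 randomised, 25% loss, 2:1 allocation, two-sided 5%, SD about 2.

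- Analysed: 380 × 0.75 = 285, that is 190 and 95.
- Standard error in SD units: √(1/190 + 1/95) = 0.1257.
- Power at 0.35 SD: Φ(0.35/0.1257 − 1.96) = 79.5%.
- Power at 0.40 SD: Φ(0.40/0.1257 − 1.96) = 88.9%.

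This reproduces the plan's 80% to 90%. No covariate enters the calculation, so the conflict does not touch it.

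**4. Precision under each covariate**

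The SAP gives no correlation between follow-up BPI and either baseline. Assume absolute correlations of 0.5-0.6 for baseline BPI and 0.3-0.5 for baseline OKS. The ratio of residual variances, OKS model to BPI model, is (1 − r²_OKS)/(1 − r²_BPI):

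| | OKS 0.3 | OKS 0.4 | OKS 0.5 |
|---|---|---|---|
| BPI 0.5 | 0.91/0.75 = 1.21 | 0.84/0.75 = 1.12 | 0.75/0.75 = 1.00 |
| BPI 0.6 | 0.91/0.64 = 1.42 | 0.84/0.64 = 1.31 | 0.75/0.64 = 1.17 |

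The range is 0% to 42% extra variance. With SE = 2 × √(1 − r²) × 0.1257 and a true difference of 0.7 points:

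| r | SE (points) | Power |
|---|---|---|
| none | 0.251 | 79.5% |
| 0.3 | 0.240 | 83.1% |
| 0.4 | 0.230 | 86.0% |
| 0.5 | 0.218 | 89.5% |
| 0.6 | 0.201 | 93.6% |

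**5. How often the choice would change a result**

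Both models were fitted to the same simulated trials: 4,000 per setting, 190 against 95, true difference 0.7. Assumed correlations with follow-up BPI were 0.5-0.6 for baseline BPI and −0.4 to −0.5 for baseline OKS, and −0.6 to −0.7 between the two baselines. Within a trial the two estimates differed with an SD of 0.09 to 0.12 points, and the models disagreed on p < 0.05 in about 6% to 10% of trials. The simulation had no centre effect and did not reproduce the minimisation, so these figures are only a guide.

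**The case against.** The strongest reply is that this is a template footnote and that nobody would be misled. Section 1 calls the shells a guide, and every statement of the models in the text points to BPI or to the outcome's own baseline. The shells carry other copying slips: Table 31 is captioned Severity under an Interference heading, Tables 32-33 are captioned as missing-data analyses but show per-protocol and CACE results, and section 7.6.1 sends the overlap results to Tables 32-33 although they stand in Tables 30-31.

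Much of this stands. A reader might infer that the SAP pre-specifies two primary analyses of equal standing, and the documents do not support that. A carried-over footnote is the likelier explanation, though the SAP does not say so. The reply does not remove the conflict: section 1 also holds the reported content to the shells, and the covariates behind an estimate are content, not layout.

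A reader might also infer that standard errors from the OKS model would be invalidly large because the minimisation factors are left out. The calculation above shows only what a weaker covariate costs in precision. Conservative standard errors after minimisation are a separate matter, and nothing here quantifies them.

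**Conclusion.** The contradiction is real and unresolved. It concerns the definition of both co-primary estimates, and the SAP's own text and design favour baseline BPI.

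Its consequence is limited. Under randomisation both estimators are unbiased, so a reading of bias is not supported. Nor is a reading that the trial would be underpowered: the planned power is unadjusted, and under the assumed correlations the OKS model still gives 83% to 90% at 0.35 SD, above the unadjusted 79.5%. What remains is freedom to choose the primary model after the data are seen, and a loss of precision between nothing and 42% extra residual variance. That range, and the 6% to 10% disagreement on significance, rest wholly on assumed correlations. The contradiction itself needs no assumption.

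**What to change.** - Tables 14, 17-18 and 30-33: change the footnote to trial centre and baseline BPI. Table 15: the same, plus time to assessment clinic.
- Secondary-outcome tables (16, 19-29, 34-44): change the footnote to centre, baseline BPI and the outcome's own baseline, as in section 7.4.2. Check that the marker in Table 16 also covers the differences in means.
- Sections 7.3 and 7.4.2: state which baseline BPI score or scores enter each model. Section 7.3 uses the plural and section 7.4.2 the singular, so the matching subscale and both subscales are each possible readings. Including both would match the minimisation factors.
- Record the change in Table 51.

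The cost is wording only. All the variables are already in the baseline tables, and no sample-size figure changes.

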7.6.4 Repeated measures analysis

A repeated measures analysis will be performed using a multi-level mixed effects linear regression to model each of the BPI subscales (measured at 6 months and 12 months) on the baseline measure of the outcome, stratification variables and any variables which show imbalance at baseline. The repeated measures model will also include an interaction between the intervention allocation and the time point. The p-value of the interaction term will be the focus of analysis. This analysis will account for clustering within patient using a random effect. The analysis will include those patients who have at least one non-missing outcome over the two time-points. The results of this analysis will be presented in **Table 45**.

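### Sections 7.3, 7.4.2 and 7.6.4 pick extra covariates by observed baseline imbalance, which makes secondary and sensitivity models data-dependent and gains no precision

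*SAP*

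**What the plan says.** Section 7.3 specifies linear regression for each co-primary outcome: "The models will be adjusted for trial centre as a fixed effect and baseline BPI pain scores". It then adds an imbalance step: "Primary analysis will be adjusted for variables which are imbalanced at baseline to see if this makes a marked difference to the unadjusted primary analysis".

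Section 7.4.2 gives the secondary-outcome models a fixed core: "The models will adjust for trial centre, baseline BPI pain score and also the baseline scores of the outcome for which it is modelling". Extra imbalance adjustment has two triggers. The first applies only "in the unlikely event that such adjustment had a material effect on the results for the primary outcomes". The second is a particular cause for concern arising from a "known strong relationship between a specific outcome and an individual variable demonstrating (chance) imbalance at baseline".

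Section 7.6.4 regresses the 6- and 12-month BPI scores on the baseline outcome, "stratification variables and any variables which show imbalance at baseline". No version without the imbalanced variables is described, and the covariate footnote to Table 45 is left open.

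Nothing in the SAP says what counts as imbalanced, as a marked difference or as a material effect, and no candidate variables are listed. The SAP also does not say which primary result is definitive if the two in section 7.3 differ.

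**The concern.** In a properly randomised trial, a baseline difference between arms is due to chance. Its size says nothing about whether the variable predicts outcome, and prognostic strength is what makes a covariate worth including. Selecting on imbalance can bring in variables of no value. It leaves out a strong predictor that happens to be balanced, although adjusting for that predictor would still reduce residual variance.

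The rule also makes models depend on the data. Under section 7.6.4 the covariates are known only once the arm-specific baseline tables have been read. Under section 7.4.2 the first trigger also needs the primary result. Because the terms are undefined, two analysts following the SAP could report different secondary estimates, and a reader could not rule out selective adjustment.

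The SAP is more careful elsewhere. Section 4.3 considers prognostic value when choosing imputation variables and finalises that list before imputing. Section 7.7.2 fixes the PaSol categories before the interaction models are run. The covariates for the effect estimates have no equivalent safeguard.

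**Working it through.** **Inputs.** Section 3.7 gives 380 randomised, 25% loss, 2:1 allocation and a two-sided 5% level. Thus 380 × 0.75 = 285 analysed, or 190 and 95.

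**The plan's own figure.** The SAP gives no figure on covariate selection. Its power statement is checked only to confirm the sample sizes. Power = Φ(d × √(190 × 95 / 285) − 1.96), with √63.33 = 7.958.
- d = 0.35: Φ(2.785 − 1.96) = 79.5%
- d = 0.40: Φ(3.183 − 1.96) = 88.9%

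These agree with the stated 80% to 90%.

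**How often would the trigger operate?** Assume that imbalance means p < 0.05 and that the variables are independent; the SAP says neither. The chance that at least one of K variables is flagged is 1 − 0.95^K.
- K = 7 (the demographics in section 5.2): 30%
- K = 20 (Table 1 has 22 rows besides the two BPI scores): 64%

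These are illustrations. Several of the variables are correlated, and Tables 1 to 3 have no p-value column.

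**What does the rule do to the estimate?** The simulation used 6,000 trials per setting with 190:95 patients. It assumed a baseline–outcome correlation of 0.5 and 5 or 10 further covariates that jointly explain 10% or 20% of outcome variance. A covariate was flagged as imbalanced at p < 0.05. Type I error with no true effect, followed by mean standard error (SE):

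| Model | 5 covariates, 10% | 10 covariates, 10% | 10 covariates, 20% |
|---|---|---|---|
| Fixed core | 5.3%; 0.1089 | 5.1%; 0.1089 | 5.1%; 0.1089 |
| Core + imbalanced variables | 4.9%; 0.1088 | 4.8%; 0.1091 | 4.7%; 0.1087 |
| Better of these two | 5.6% | 5.7% | 5.8% |
| Core + all covariates, fixed in advance | 5.0%; 0.1023 | 5.1%; 0.1032 | 5.1%; 0.0950 |

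**Check by formula.** SE ≈ √(residual variance) / 7.958.
- Core model: √0.75 / 7.958 = 0.109
- Further 10% explained: √0.65 / 7.958 = 0.101
- Further 20% explained: √0.55 / 7.958 = 0.093

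The simulated values are slightly larger because extra terms are estimated. Fixing the covariates in advance lowers the SE by 5% (0.1032 / 0.1089 = 0.948) to 13% (0.0950 / 0.1089 = 0.872). Selecting on imbalance leaves it unchanged.

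The simulation covers a single-time-point regression. It bears on the repeated-measures model by analogy only.

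**The case against.** The strongest reply is that the primary analysis is already settled. Section 7.3 names its covariates, and the imbalance step reads as a comparison against that model. This stands. A reader might infer that the primary result itself is data-driven, but the text does not support that. What remains is that the SAP does not call the first model definitive, and it describes a model with two sets of covariates as unadjusted.

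A reader might also infer that prognostic baseline information is generally wasted. That is too broad. Centre, baseline BPI and each secondary outcome's own baseline are used whatever the balance; only other predictors depend on imbalance.

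A third tempting inference is a gain in primary power, from about 79% into the mid-80s or above. It does not follow. The 79.5% is for a comparison without covariates, the planned model already includes baseline BPI, and the fix leaves the primary model unchanged.

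Two further points are fair. Section 7.4.2 calls its first trigger unlikely, and its second does consider prognosis. Section 7.6.4 sits among the sensitivity analyses. These limit the consequences, but the second trigger still requires imbalance and names no variables, and section 7.6.4 offers no fixed alternative.

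**Conclusion.** The point holds for the secondary-outcome models, the repeated-measures model and the extra adjustment in section 7.3. Their covariates depend on observed imbalance under undefined terms, and for the secondary outcomes partly on how the primary result moved. The rule gained no precision in simulation, whereas fixing prognostic covariates in advance cut the SE by 5% to 13%. That range rests on an assumed baseline correlation of 0.5 and an assumed 10% to 20% of further explained variance; the SAP gives neither.

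The effect on type I error is small. Imbalance selection alone gave 4.7% to 4.9%, and always taking the better of two results gave 5.6% to 5.8%. The matter is one of pre-specification and precision, and it does not threaten the validity of the primary test. It deserves correction because the remedy is cheap.

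**What to change.** 1. In section 7.3, state that the model with centre and baseline BPI is the definitive primary analysis, and stop calling it unadjusted. Separately, reconcile the Table 14 footnote, "Adjusted for trial centre and baseline OKS", with section 7.3, because the mismatch leaves the fixed core unclear.
2. In section 7.4.2, delete both triggers for imbalance adjustment. Keep centre, baseline BPI and the outcome's own baseline.
3. In section 7.6.4, delete the imbalance clause. Use centre and both baseline BPI scores, one of which is the outcome's own baseline, and complete the Table 45 footnote to match.
4. Replace the imbalance check in section 7.3 with one adjusted sensitivity model. Fix its extra covariates on prognostic grounds before unblinded data are seen. Age and sex are natural examples, since section 4.3 already places them in the imputation model. Use the same set if secondary or repeated-measures models are adjusted further.

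The cost is SAP wording, a few degrees of freedom, and a stated way of handling missing baseline covariates so that the complete-case analysis does not lose patients. A long covariate list is not needed.
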